1 BACKGROUND

As of 14 October 2020, the WHO European region had reported over 7 million COVID-19 cases and almost 250,000 deaths [1]. At the time of initiating this study, although the number of reported cases has been lower in the African region (just over 1.2 million), likely due to both later arrival of the pandemic and incomplete reporting, over half of these have been in South Africa and over 18,000 COVID-19 deaths have been reported in the country [1].

Seroprevalence studies provide estimates of the percentage of the population that has either been infected with SARS-CoV-2 (the virus which causes COVID-19) or vaccinated against the virus, based on evidence of antibodies against the viral spike (S) or nucleocapsid (N) proteins. However, few published studies have included data from children and adolescents [2, 3]. The prevalence of antibodies to SARS-CoV-2 in children in (pre-vaccination) population studies has been estimated as ~3-4% in those aged 0-19 in Spain by mid-May 2020 [2], and 0.8% in 5-9 year-olds and 9.6% in 10-19 year-olds in Geneva by early May 2020 [3]. In England, seroprevalence in 1-24 year olds has been estimated as 5.2% (95% credible interval 3.2-7.8%) based on samples collected between May and August 2020 [4]. Whilst uncertainties remain about the extent and duration of protection that antibodies may provide, measuring seroprevalence is a first step towards understanding the proportion of a population that remains susceptible to infection and therefore the potential risk of future outbreaks.

There are currently limited and inconsistent data on the epidemiology of SARS-CoV-2 and COVID-19 in people living with HIV. The studies published to date have presented data on COVID-19 amongst adults living with HIV [5-11] but it remains unclear to what extent HIV affects the risk of infection, disease, severe disease or death. Some studies suggested that there may not an association between HIV and COVID-19 severity or mortality [5], whilst others suggest increased mortality amongst adults with COVID-19 co-infected with HIV compared to the HIV-uninfected population, even after adjustment for co-morbidities and other factors [11, 12]. These studies have not included children.

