3 STUDY PROCEDURES

3.1 STUDY DESIGN

This is a serial point prevalence survey of representative samples of children and adolescents attending routine HIV care in the participating clinics and cohorts, with repeat antibody testing at baseline (study entry) and approximately 6 months after study entry (Table 1), and in some clinics further long-term follow-up through linkage to data collected in an ongoing longitudinal cohort study. In South Africa approximately 50-100 HIV-uninfected adolescents enrolled in the ongoing CTAAC cohort will be invited to participate in this study as a comparator group.

Eligible participants who are interested in joining the study will be asked for their consent to participate if aged ≥ 16 years or as per local legal requirements. For participants aged <16 years, consent of their parent/carer will be sought as per legal requirements. Assent will be sought from children and adolescents aged 10 years and older, depending on local ethics requirements. Potential participants and their parents / carers should be allowed at least 5-10 minutes to consider whether or not to take part; where possible, it may be helpful to give patients copies of the participant information sheet while they wait for their appointment.

Data collection will be conducted at HIV clinics during routine visits in clinical care (in the European cohorts) or planned study visits (in CTAAC, for both CLWHIV and HIV-uninfected adolescents), and no additional study visits will be required.

At entry to the study the participant will give a venous blood sample for a SARS-CoV-2 antibody test (the exact test used will depend on local clinical practice). An additional serum sample will be taken at the same time as a routine blood draw and leftover sample will be used if possible. At the next scheduled routine HIV clinic/study visit approximately 6 (no less than 3 and up to 13) months later, a repeat venous blood sample will be collected for a second antibody test. At each visit, participants (or their parents/carers) will be given a COVID-19 questionnaire, asking short questions about any COVID-19 diagnoses in themselves or among household members and other possible exposures to the virus. All study procedures will be carried out following local COVID-19 guidelines.

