3.4 LABORATORY TESTING

Where sites are conducting serological testing as part of standard care, venous blood samples taken at each site will be transported to the laboratory(ies) routinely carrying out antibody testing for that site. Samples will be analysed with the tests used by each site in routine practice according to manufacturers' instructions or, if in-house tests are used, local SOPs/protocols.

At sites not offering routine serological testing, arrangements should be made with local laboratories for testing. There is strong preference for tests for IgG against the viral spike protein as data suggests this has the longest half-life; however, it is recognised that there may be local considerations influencing the range of tests available across settings and results from other tests will be considered.

Where possible, antibody test results will be reported both categorically (e.g. positive, negative, equivocal) and quantitatively (e.g. antibody titre). Results will be transferred securely as described in Section 4.2.

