6.2 ANALYSIS PLAN

Data will initially undergo extensive logic and consistency checks and any potential errors will be resolved through discussion with cohort/clinic data managers.

Proportions with SARS-CoV-2 antibody at baseline and follow-up and the number/incidence of changes in antibody status between baseline and subsequent test will be estimated overall and by key patient characteristics, region, history of symptomatic COVID-19, contact with COVID-19 cases, receipt of COVID-19 vaccine. Factors associated with the presence of SARS-CoV-2 antibody, changes in

antibody status and any subsequent COVID-19 diagnosis (if numbers allow), will be explored using univariable and multivariable logistic and Poisson regression. Exposures of interest include age, sex, ART class and regimen (e.g. protease inhibitor- or tenofovir-based versus other), CD4 count, viral load, ethnicity, BMI-for-age z-score, co-infections (e.g. tuberculosis), co-morbidities, receipt of/duration since COVID-19 vaccine and household size.

The association between HIV status and SARS-CoV-2 seropositivity, changes in antibody status and subsequent COVID-19 diagnosis will be assessed in the South African cohort (which includes HIV-uninfected children as well as CLWHIV) using similar methods. Directed acyclic graphs may be used to determine which covariates to include in the models and to aid interpretation of the results.

If there is substantial variation in the type of antibody test used (anti-S versus anti-N), analyses will be stratified by type of test. For participants with positive results at both baseline and follow-up and if data allow, quantitative antibody results will be explored to qualitatively describe the possible contribution of re-exposure boosting antibody responses (versus persistence of an existing response).

In sensitivity analyses, we will investigate the implications of misclassification of results due to imperfect sensitivity / specificity of the serological tests used.

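### Anti-S and anti-N results can be pooled in the vaccine analyses and overall prevalence, although an anti-N test would miss the response to a spike-only vaccine

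*Combined protocol and SAP*

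**What the plan says.** **Choice of test.** The assay is local: section 3.1 says "the exact test used will depend on local clinical practice". Section 3.4 states a preference and its reason, "There is strong preference for tests for IgG against the viral spike protein as data suggests this has the longest half-life", then adds that "results from other tests will be considered". The reason given is antibody persistence, not detection of a vaccine response. Section 6.2 names anti-N as one of the expected targets.

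**Vaccinated participants.** Section 2.2 keeps participants who are vaccinated after enrolment. Section 1.2 lists vaccine receipt among the factors in a secondary objective. Section 6.2 breaks down prevalence and status change by vaccine receipt, and its model exposures include "receipt of/duration since COVID-19 vaccine and household size".

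**Handling of test type.** Section 6.2: "If there is substantial variation in the type of antibody test used (anti-S versus anti-N), analyses will be stratified by type of test". It also plans a sensitivity analysis for imperfect test performance, without mention of vaccination.

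**Data.** Table 2 in section 4.1 collects type of test and vaccine receipt at each visit.

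Nothing in the plan links the antigen a test targets to the participant's vaccination status.

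**The concern.** A vaccine that presents only spike does not raise antibody to nucleocapsid. For a vaccinated participant who was never infected, an anti-N test is therefore negative however strong the vaccine response, whereas an anti-S test can detect it. The two kinds of result answer different questions in vaccinated people, yet the plan may combine them.

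Three results are exposed:

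- **Vaccine associations.** Positivity among the vaccinated, and the terms for receipt and time since vaccine, are pulled toward no effect. Section 1 points out how little is known about vaccine response in people living with HIV, so a diluted association could easily be misread as poor response.
- **Overall antibody prevalence and its change over time.** As vaccination spreads between the two tests, pooled prevalence rises less than it should.
- **Changes in status.** Under section 3.1 the first result may come from routine care, another study or stored blood, so a participant's two tests may have different targets. An anti-S positive followed by an anti-N negative could be counted as antibody loss, and the opposite order as a gain.

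**Working it through.** **The plan's own figure.** Section 6.1 assumes 10% prevalence and states 95% half-widths of 2 points in Europe and 3 in South Africa. With 1.96 × √(p(1−p)/n) and p = 0.10, n = 650 gives 2.31 points and n = 500 gives 2.63 points. The stated figures reproduce to the whole percent and are not in dispute.

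**Inputs for the illustration**
- Infected, π = 10%: the prevalence assumed in section 6.1.
- Vaccinated, v = 5%, 10% or 30%: assumed, and taken as independent of infection.
- Anti-S response to vaccine, r = 97%: assumed.
- Share of results that are anti-N only, f = 10% or 20%: assumed, as shares that might stay pooled.
- Spike-only vaccine and otherwise perfect tests: assumed.

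**Positivity among the vaccinated**
- Anti-S: 1 − (1−π)(1−r) = 1 − 0.90 × 0.03 = 97.3%.
- Anti-N: π = 10%.
- Pooled, (1−f) × 97.3% + f × 10%:
  - f = 10%: 87.57 + 1.00 = 88.6%, about 89%.
  - f = 20%: 77.84 + 2.00 = 79.8%, about 80%.

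**Prevalence in the whole sample**
- Anti-S: S = 1 − (1−π)(1−v·r). At v = 10%, 1 − 0.90 × 0.903 = 18.7%. At v = 30%, 1 − 0.90 × 0.709 = 36.2%.
- Anti-N: 10% at any v.
- Shortfall from pooling: f × (S − π) = f × (1−π) × v × r = 0.873 × f × v.

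| Vaccinated | f = 10% | f = 20% |
|---|---|---|
| 0% | 0 | 0 |
| 5% | 0.4 points | 0.9 points |
| 10% | 0.9 points | 1.7 points |
| 30% | 2.6 points | 5.2 points |

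**If stratification is triggered.** The anti-S stratum is free of this bias. In the anti-N stratum, vaccinated and unvaccinated participants are both 10% positive, so the vaccine odds ratio is 1 whatever the true response.

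**Why the sensitivity analysis does not cover this.** The error depends on vaccination status. An anti-N test may detect past infection well and still miss every spike-only vaccine response. A single sensitivity value per assay cannot represent both, and the main estimate would be unchanged in any case.

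**The case against.** The plan does recognise the difference between targets. It prefers anti-spike tests strongly, provides for stratification, and adds a misclassification analysis. Where most results are anti-S, or where stratification is applied, the anti-S estimates are sound. A null vaccine term in an anti-N stratum is also a correct description of anti-N. All this stands, but no element refers to vaccination, and the stratification trigger is undefined.

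Several stronger readings are tempting but unsupported:

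- *That the endpoint is defined as infection or vaccination.* The words "has either been infected with SARS-CoV-2 (the virus which causes COVID-19) or vaccinated against the virus" come from the Background and describe seroprevalence studies in general. The primary objective refers only to the prevalence of antibodies, and vaccine response is not a separate objective. The vaccine analyses in section 6.2 are explicit, however, and their dilution does not depend on the Background wording.
- *That every vaccinated participant tested by anti-N is scored negative.* Those who were also infected can be anti-N positive. In the illustration, 10% are.
- *That the plan interprets such negatives as vaccine non-response.* It does not say so. The risk lies in how pooled results would be read.
- *That the bias clearly exceeds the study's precision.* The 2 to 3 point half-widths apply at 10% prevalence. At 30% vaccinated and f = 10%, pooled prevalence is 36.2 − 2.6 = 33.6%, and the half-width is about 3.6 points for n = 650 and 4.1 for n = 500. The 2.6-point shortfall lies within both.
- *That large anti-N shares would be pooled.* A 40% share would ordinarily count as substantial variation and trigger stratification. The small shares most likely to stay pooled produce the smallest bias.

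Low uptake is also plausible. The study includes children, and the only vaccine priority group described (section 1) is people with HIV aged 16 and over in the UK.

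**Conclusion.** The point holds in conditional form. As written, section 6.2 allows anti-N results to be pooled into vaccine-related estimates and overall prevalence. If the vaccines are spike-only, the effect is downward bias in both, and status changes can be spurious where a participant's two tests have different targets. Under the assumptions above, positivity among the vaccinated falls by about 9 points at a 10% anti-N share (97.3 − 88.6) and about 18 points at 20% (97.3 − 79.8). The prevalence shortfall runs from zero with no vaccination to 5.2 points at 30% vaccinated and 20% anti-N.

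The documents give neither vaccine type, uptake nor anti-N share, so the true size is unknown. The vaccine associations are the most exposed, because their dilution does not shrink when uptake is low. This is an improvement that should be made, because the rule is cheap and uses data already collected. It does not show that the study's prevalence estimates are wrong.

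**What to change.** Amend section 6.2 so that the following applies regardless of how much test type varies:

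1. Estimate prevalence and status change by vaccine receipt, and all terms for vaccine receipt and time since vaccine, from anti-S results only. Use a status change only where both tests are anti-S.
2. Once vaccination has begun, report any-antibody prevalence (from infection or vaccine) from anti-S results. Report anti-N results separately, as evidence of infection.

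Do not simply recode the anti-N negatives of vaccinated participants as not assessable. Exclusion would then depend on the result. At 30% vaccinated, 0.30 × 0.90 = 27% of an anti-N site's participants would be dropped, and the site would read 10/73 = 13.7% against 36.2% on anti-S. The pooled shortfall would still be 1.7 points at f = 10% (36.2 − 33.57/0.973) and 3.5 points at f = 20% (36.2 − 30.95/0.946), instead of 2.6 and 5.2.

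**Cost.** A paragraph of analysis wording and no new data, provided that the recorded test type identifies the target antigen. The sample for these analyses is smaller, and sites that used only anti-N do not contribute to them.

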7 REGULATORY & ETHICAL ISSUES

7.1 COMPLIANCE

The study will be conducted in compliance with the approved protocol, the Declaration of Helsinki 1996, the principles of Good Clinical Practice as laid down by the ICH topic E6 (R2), General Data Protection Regulation and the UK Data Protection Act 2018 (DPA number: Z6364106), and the UK Policy Framework for Health and Social Care Research.

Each cohort is responsible for ensuring compliance with local and national regulatory and ethical processes, and data protection.

7.1.1 DATA COLLECTION AND RETENTION

Collected data are pseudonymised: no names, initials, hospital numbers, national ID or addresses of patients are collected. All participants are assigned a unique study identification number, linkable to individual patients only by the individual cohort study staff entering the data. The Principal Investigators (PIs) of each cohort ensure that participant anonymity is maintained and that their identities are protected from unauthorised parties.

Clinical notes and administrative documentation are retained at participating centres according to local data retention and storage requirements. The MRC CTU at UCL will not receive copies (hard or electronic) of patient notes.

The study dataset will be stored at the MRC CTU at UCL, and a final copy will be sent to the study sponsor, Penta. The dataset will be held for a minimum of 5 years after the end of the study and then archived for up to 20 years initially. Although this study will end after 18 months, longer term outcomes may be ascertained through ongoing follow-up in the EPPICC cohorts (subject to funding and approvals).

Signed consent / assent forms will be stored securely at participating clinics.

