3.2 ENROLMENT AND FOLLOW-UP

We aim to start enrolment from November 2020 (pending ethics approval) and enrol participants for approximately twelve months or until the sample size is met. The enrolment period may be extended in the event of disruptions to clinic services due to COVID-19. Where feasible, all children and adolescents meeting the inclusion criteria and attending the participating clinics during this period will be invited to take part; where this is not possible, a convenience sample of children and adolescents (e.g. those attending clinic on a specified day of the week) should be invited. The invitation to participate should be independent of the patient's probability of having been exposed to COVID-19.

Participants will be considered lost to follow-up for the purposes of this study if they have not provided the second blood sample by 13 months after the enrolment date.

Participants enrolled in the EPPICC Paediatric Study or CTAAC will continue to be followed up as part of the ongoing study.

Logs will be kept of the number of children and adolescents declining the invitation to participate, with reasons for refusal where available.

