6 STATISTICAL CONSIDERATIONS

6.1 SAMPLE SIZE

The total sample size is 1150, with provisional numbers eligible by cohort summarised in Table 3. Allowing for 70% participation, the target sample size can be met within the participating cohorts. At some sites within EPPICC, participants will receive SARS-CoV-2 serological tests as part of routine care or within an ongoing research study, and a repeat test will be offered as part of this study approximately six months after (no less than 3 and up to 13 months) the first sample; however both sets of results will be collected in this study. At other sites and in South Africa, both tests will be part of this study.

In addition, some sites may be able to test stored samples taken for other purposes and not previously tested for SARS-CoV-2 antibodies. In these cases, this would be considered the first test and the participant would have one additional test as part of this study approximately six months (no less than 3 and up to 13 months) after the first sample date.

Table 3: Provisional numbers of eligible participants (aged <25 years) per cohort

Cohort	Number of eligible participants	
	CLWHIV	HIV-uninfected adolescents
Belgium	74	0
Greece	22	0
CoRISPES (Spain)	250	0
CoRISPE-Cat (Spain)	50	0
Sweden	85	0
Ukraine	170	0
United Kingdom	442	0
EPPICC Total	1093	0
South Africa	400	50-100
Total	1493	50-100

Assuming an overall anti-SARS-CoV-2 prevalence of 10%, similar to that reported for children aged 10-19 years in Geneva, Switzerland [3], the sample size would result in a 95% confidence interval of +/- 2% in Europe and +/-3% in South Africa.

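### Does the stated 18-month duration conflict with a closure rule that can keep the study open to about month 25?

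*Combined protocol and SAP*

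**What the plan says.** The duration appears twice. The Summary lists 18 months, and section 7.1.1 has the clause "Although this study will end after 18 months", which leads into a remark that longer-term outcomes may still come from the EPPICC cohorts.

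The timing rules are elsewhere:

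- **Enrolment (section 3.2).** The plan is to "enrol participants for approximately twelve months or until the sample size is met". It adds: "The enrolment period may be extended in the event of disruptions to clinic services due to COVID-19".
- **Second sample (section 3.1).** At the next scheduled visit, "approximately 6 (no less than 3 and up to 13) months later, a repeat venous blood sample will be collected". Section 6.1 gives the same window for participants first tested in routine care or another study: "approximately six months after (no less than 3 and up to 13 months) the first sample".
- **Loss to follow-up (section 3.2).** Participants count as lost "if they have not provided the second blood sample by 13 months after the enrolment date".
- **Closure (section 7.3).** The study closes once each participant who has not withdrawn consent has either two analysed samples or the status of lost to follow-up.
- **Retention (section 7.1.1).** "The dataset will be held for a minimum of 5 years after the end of the study", followed by archiving for up to 20 years initially.

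**The concern.** Read side by side, these statements give two different ends to the study. Section 7.1.1 says flatly that the study will end at 18 months, while section 7.3 lets it run until the last participant's 13-month limit has expired. Nothing in the text calls the 18 months nominal.

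Two things might be at stake. First, if a site took month 18 as a hard stop, later enrolees would lose part of the window that section 3.1 allows them. Their second samples feed the part of the primary objective that concerns change in prevalence over time. Second, the retention period is counted from the end of the study, so two readings of that end give two start dates.

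**Working it through.** **Inputs.** Enrolment of about 12 months (3.2). Second sample nominally at 6 months, window 3 to 13 months (3.1, 6.1). Loss to follow-up at 13 months after enrolment (3.2). Stated duration of 18 months (Summary, 7.1.1).

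**Formula.** Duration = enrolment period + time from the last enrolment to the second sample or to loss to follow-up.

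| Case | Calculation | Months after first enrolment |
|---|---|---|
| Plan's own figure, nominal visit | 12 + 6 | 18 |
| Earliest permitted second sample | 12 + 3 | 15 |
| Latest under 7.3 with the 13-month limit | 12 + 13 | 25 |

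The stated 18 months is reproduced exactly by the nominal schedule. The gap to the latest closure is 25 − 18 = 7 months. The full 13-month window fits inside 18 months only for those enrolled by month 18 − 13 = 5. Someone enrolled at month 12 would have 18 − 12 = 6 months, which is the nominal interval.

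**The 25 is not a ceiling.** Section 3.2 sets no maximum on an extension of enrolment. For illustration, extensions of 3 and 6 months (assumed) give 12 + 3 + 13 = 28 and 12 + 6 + 13 = 31. Closure also waits for samples to be analysed, not only taken.

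**Nor is it the expected date.** Closure comes sooner if second visits fall near 6 months or if enrolment stops early on reaching the target. Participants whose first test was an earlier or stored sample give only one further sample, so they need not hold the study open for a later visit.

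**Which statement governs.** The clause in 7.1.1 is subordinate: its purpose is to say that follow-up can continue through the cohorts. No section stops sampling or data capture at month 18. Section 4.2 has cohorts submit either in real time or once the last patient's follow-up has finished, which is an event and not a fixed month. Section 7.3 is headed as the closure rule and is the only text that says what ends the study.

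**Consequences under 7.3.** Every second sample inside the window is kept. The proportions at each visit, the changes in antibody status and the regression models in 6.2 do not use the study duration, and neither does the sample size in 6.1. The retention start can move by up to 7 months with 12-month enrolment, against a minimum of 5 × 12 = 60 months and archiving beyond that.

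**The case for a change.** The strongest case for a change is that 7.1.1 says the study will end, not that it is expected to. The 13-month limit is also deliberate: it appears in 3.1, twice in 6.1 and again as the loss-to-follow-up limit in 3.2. The 18 months leaves no slack. Under 7.3 it takes only one participant who enrols after month 5, still needs a second sample and neither returns nor withdraws to keep the study open past month 18. In a study planned for 1150 participants that is likely to happen, so 18 months is probably too short as a forecast of formal closure. Early completion of enrolment need not remove the gap. In Europe, for example, 70% of 1093 eligible is 765. With even accrual over 12 months (an assumption), 650 would be reached at 650/765 × 12 = 10.2 months, so the latest closure would be 10.2 + 13 = 23.2 months. Rewording two lines would cost almost nothing.

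Most of this stands: the arithmetic is right and the text is not reconciled. What does not stand is the step from there to a defect in the plan. A forecast that proves short alters nothing when the operative rule is tied to events. The harm from a literal month-18 cut-off needs a site to apply a rule that the protocol never states. The documents give no non-return rate and no accrual pattern, so the number of samples exposed to that misreading cannot be derived, and it could be zero.

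**Conclusion.** The concern does not call for a change. The 18 months is the nominal plan, 12 + 6. Under section 7.3 the study may formally close as late as about month 25 with 12-month enrolment, and later if enrolment is extended or analysis is pending. The difference of up to 7 months affects a planning figure and the start of a minimum retention period. It does not affect the second-sample window, the data available for the primary objective, the precision or any analysis.

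This rests on reading 7.3 as the rule that ends the study. That is the natural reading, because it is the only closure rule and no section imposes a sampling stop at month 18. Describing 18 months as nominal would be tidier, but it would change nothing the study does, estimates or concludes.
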